5.1 Imputation rules

5.1.1 AE date imputation

The following table explains the notation used in the logic matrix. Please note that **missing start dates** will not be imputed.

	Day	Month	Year
Partial Adverse Event Start Date	Not used	MON	YYYY
Treatment Start Date (TRTSTD)	Not used	TRTM	TRTY

The following matrix explains the logic behind the imputation.

	MON MISSING	MON < TRTM	MON = TRTM	MON > TRTM
YYYY	NC	NC	NC	NC
MISSING	Uncertain	Uncertain	Uncertain	Uncertain
YYYY < TRTY	(D)	(C)	(C)	(C)
	Before Treatment Start	Before Treatment Start	Before Treatment Start	Before Treatment Start
YYYY = TRTY	(B)	(C)	(A)	(A)
	Uncertain	Before Treatment Start	Uncertain	After Treatment Start
YYYY > TRTY	(E)	(A)	(A)	(A)
	After Treatment Start	After Treatment Start	After Treatment Start	After Treatment Start

The following table is the legend to the logic matrix.

If AE end date is complete and AE end date < Treatment start date or AE end date is partial and AE imputed end date < Treatment start date, then AE start reference = min (informed consent date, earliest visit date from SV) Else if AE end date is partial, AE end date > = Treatment start date or AE is ongoing, then AE start reference = treatment start date.

Relationship		Time imputation
Before AE start reference	Partial date indicates AE start date prior to AE start reference	
After AE start reference	Partial date indicates AE start date after AE start reference	
Uncertain	Partial date insufficient to determine relationship of AE start date to AE start reference	

Relationship		Time imputation
Imputation Calculation		
NC/Blank	No convention	
(A)	MAX(01MONYYYY, AE start reference+1 day)	
(B)	AE start reference+1	
(C)	15MONYYYY	
(D)	01JULYYYY	
(E)	01JANYYYY	
Complete date	No date imputation	If time is cuptured for the study Case1: if AE start date is not equal to AE start reference then do the following: If minutes missing then AESTMF = M and time is imputed to hh:00 If minutes missing then AESTMF = H and time is imputed to 00:00 Case2: if AE start date = AE start reference then AESTMF = H and time is imputed to treatment start time + 1 hour

Adverse Event End Date Imputation

Imputed date = date part of original date, if complete date

Imputed date = min (completion/discontinuation visit date, DEC 31, date of death), if month is missing

Imputed date = min (completion/discontinuation visit date, last day of the month, date of death), if day is missing

Adverse Event End Time Imputation

If the AE end date is complete and time is captured in the study then:

Case 1. if AE end date is not equal to Treatment end date, then do the following:

if minutes missing then time is imputed to hh:00 if time missing then time is imputed to 00:00

Case 2: if AE end date = Treatment end date then time is imputed to treatment end time

If the AE end date is partial then end time is imputed to 00:00.

Imputed Date Flag

If year of the imputed date is not equal to YYYY then date flag = Y

else if month of the imputed date is not equal to MON then date flag = M

else if day of the imputed date is not equal to day of original date then date flag = D

else date flag = null

Imputed Time Flag

If hours of the imputed time is not equal to hours of original time then time flag = H

else if minutes of the imputed time is not equal to minutes of original time then time flag = M else time flag = null.

5.1.2 Concomitant medication date imputation

This algorithm is used when event is the partial start date of the concomitant medication.

The following table explains the notation used in the logic matrix. Please note that **missing start dates** will not be imputed.

	Day	Month	Year
Partial CM Start Date	Not used	MON	YYYY
Treatment Start Date (TRTSDT)	Not used	TRTM	TRTY

The following matrix explains the logic behind the imputation.

	MON MISSING	MON < TRTM	MON = TRTM	MON > TRTM
YYYY	(C2)	(C1)	(C1)	(C1)
Missing	Uncertain	Uncertain	Uncertain	Uncertain
YYYY < TRTY	(D)	(A)	(A)	(A)
	Before Treatment Start	Before Treatment Start	Before Treatment Start	Before Treatment Start
YYYY = TRTY	(C2)	(A)	(C1)	(B)
	Uncertain	Before Treatment Start	Uncertain	After Treatment Start
YYYY > TRTY	(E)	(B)	(B)	(B)
	After Treatment Start	After Treatment Start	After Treatment Start	After Treatment Start

The following table is the legend to the logic matrix.

Relationship		
Before Treatment Start	Partial date indicates CMD start date prior to Treatment Start Date	
After Treatment Start	Partial date indicates CMD start date after Treatment Start Date	
Uncertain	Partial date insufficient to determine relationship of CMD start date relative to Treatment Start Date	
Imputation Calculation		
(A)	15MONYYYY	
(B)	01MONYYYY	
(C1 or C2)	IF relative reference start = before treatment start THEN TRTSDT-1	
	ELSE IF relative reference start = `` THEN TRTSDT+1	
(D)	01JULYYYY	
(E)	01JANYYYY	

Concomitant Medication End Date Imputation

If not ongoing then -

Imputed date = date part of CMENDTC, if complete date

Imputed date = min(completion/discontinuation visit date, DEC 31), if month is missing, (C2, D, E)

Imputed date = min(completion/discontinuation visit date, last day of the Month), if day is missing. (A, B, C1)

Concomitant Medication Date Flag

If not a complete date then

Y - If year of the imputed date is not equal to YYYY else M - If month of the imputed date is not equal to MON else D.

5.1.2.1 Prior therapies date imputation

Not applicable.

5.1.2.2 Post therapies date imputation

Not applicable.

5.1.2.3 Other imputations

Not applicable.

5.2 AEs coding/grading

Not applicable.

5.3 Laboratory parameters derivations

Not applicable.

5.4 Statistical models

5.4.1 Primary analysis

The SAS procedure PROC LOGISTIC, will be used to perform Logistic regression with the following sample SAS code:

PROC LOGISTIC DATA = \dots ;

CLASS usubjid acenter trtpn region smkst bmi .. / param=glm;

MODEL aval = trtpn region smkst bmi bl..;

LSMEANS trtpn / diff cl exp;

Ods output diffs=lsm_diff;

RUN;

In cases where separation is a concern, e.g. 0% response in one cohort, an exact logistic regression model will be applied. To ensure convergence, this model will not include any continuous covariates.

PROC LOGISTIC DATA = exactonly;

CLASS usubjid acenter trtpn region smkst bmi .. / param=glm;

MODEL aval = trtpn region smkst bmi bl..;

EXACT trtpn / estimate=both;

Ods output exactoddsratio=exactoddsratio;

RUN;

The SAS procedure PROC FREQ using Z-test with riskdiff option, will be used to derive Confidence intervals for response rates with the following sample SAS code:

PROC FREQ DATA =;

BY visit;

TABLES trtan*resp / riskdiff;

RUN;

From above code, we can get confidence interval for difference of proportion in PASI90 response between cohorts and also Confidence interval for proportion of PASI90 for individual cohort.

5.4.2 Key secondary analysis

Not applicable.

5.4.3 Secondary analysis

The SAS procedure PROC FREQ with Method= NEWCOMBE option, will be used to derive Confidence intervals for response rates with the following sample SAS code:

PROC FREQ DATA = \dots ;

BY visit;

TABLES trtan*resp / riskdiff (column=2 cl=(NEWCOMBE));

RUN;

The SAS procedure PROC MIXED will be used for linear mixed model for repeated measurements (MMRM) analysis with the following sample SAS code:

PROC MIXED DATA=dataset noclprint;

CLASS cohort vis1n usubjid MissingPattern;

MODEL Changes= cohort week0 dropout visit prop_score

cohort*visit cohort*MissingPattern;

REPEATED visit/subject=usubjid TYPE=cs;

LSMEANS cohort*visit/pdiff cl;

RUN;

The SAS procedure PROC PHREG, will be used to perform computed using a stratified Cox proportional hazards regression model with Cw6 group and baseline PASI as explanatory variable with the following sample SAS code:

PROC PHREG DATA=....;

CLASS trtpn baseline ..;

MODEL var*censor(0)= trtpn base.../rl ties=efron ;

RUN;

The SAS procedure PROC LIFETEST, will be used to perform log-rank test and to plot Kaplan-Meier estimates of the cumulative rate for each cohort with the following sample SAS code:

PROC LIFETEST DATA=... PLOT;

TIME timevar*censor(0);

STRATA ...;

RUN;

The SAS procedure PROC CORR, will be used to perform Spearman's (or Pearson's product moment correlation depending on data distribution) correlation with the following sample SAS code:

PROC CORR DATA = pearson/spearman OUTP=CORR;

VAR VAR1 VAR2;

RUN;

The SAS procedure PROC UNIVARIATE with NORMAL option, will be used to check the normality with the following sample SAS code:

PROC UNIVARIATE DATA = normal;

VAR var.../options...;

CLASS var;

RUN;

The SAS procedure PROC UNIVARIATE, will be used to perform Wilcoxon signed rank test with the following sample SAS code:

PROC UNIVARIATE DATA =;

VAR var...;

RUN;

The SAS procedure PROC TTEST, will be used to perform paired t-test with the following sample SAS code:

PROC TTEST;

PAIRED VARbefore*VARafter;

RUN;

The SAS procedure PROC FREQ with EXACT statement equal to MCNEM or AGREE will be used to perform Mc Nemar's test with the following sample SAS code:

PROC FREQ DATA =;

TABLES trtan*resp;

EXACT MCNEM or AGREE;

RUN;

SAS code for poisson regression model

proc genmod data=demo_ae ;

class cw6 sex age_group/ param = glm;

model numev = cw6 age_group sex / type3 dist=poisson;

lsmeans cw6 /ilink cl diff;

lsmeans age_group /ilink cl diff;

lsmeans sex /ilink cl diff;

run;

proc genmod data=demo_ae ; class cw6 (param = ref ref = "NEGATIVE") sex (param = ref ref = "M") age_group (param = ref ref = "<=40 years"); model numev = cw6 age_group sex / type3 dist=poisson ; estimate "IRR Cw6 (POS vs NEG) " cw6 1 -1; estimate "IRR Age (>40 vs <=40)" age_group 1 -1; estimate "IRR Sex (Female vs Male)" sex 1 -1;

run;

PASI Changes vs baseline: Linear Mixed Model for Repeated Mesurements (MMRM):

The SAS procedure PROC MIXED will be used in the analysis, in particular:

proc mixed data=dataset noclprint;

class cohort vis1n usubjid MissingPattern;

model Changes= cohort week0 dropout visit prop_score

cohort*visit cohort*MissingPattern;

repeated visit/subject=usubjid type=un;

lsmeans cohort*visit/pdiff cl;

run;

where changes includes all changes vs week 0 of PASI; the dropout variable is the missing pattern (i.e. a categorical variable with values of 1, 2, 3 etc.. representing completers, 1 assessment missing, 2 assessments missing, 3 assessment missing etc. in considered dependent variable –e.g. PASI); the prop_score variable is the propensity score. In order to take all the confounding factors into account, the propensity score methodology will be applied and will be included in the final model, as described above. Propensity score will be derived using logistic regression model considering cohort as the dependent variable and baseline covariates as the factors in the model. The derived propensity score will be used as the covariate in the MMRM model.

MMRM with MI approach

Multiple imputation will be performed in SAS using the following three-stage approach:

PROC MI will be applied for each PASI change (or each post baseline PASI score) containing some missing values, which results in creation of multiple copies of this dataset. All copies contain identical values of the non-missing data items, but different values imputed for missing items. The following SAS statement will be used:

proc mi data=PASI_in out=PASI_out seed=1425;

var cohort Baseline PASI score PASI score at week 1 PASI score at week 2 PASI score at week 3 PASI score at week 4 PASI score at week 8 PASI score at week 12 PASI score at week 16 PASI score at week 20 PASI score at week 24;

class cohort;

monotone regression;

run;

where variables PASI score at week 1 PASI score at week 2 PASI score at week 3... PASI score at week 24 contain missing values for some patients at each PASI time point, which PROC MI will impute using linear regression models.

Then we can calculate changes vs. baseline at each time point

```
data PASI in out1;
```

set PASI_out;

visit="Week 1"; change= PASI score at week 1 – Baseline PASI score; output;

visit="Week 2"; change= PASI score at week 2 - Baseline PASI score; output;...

visit="Week 24"; change= PASI score at week 24 - Baseline PASI score; output; run;

and then we will perform the ANCOVA model using the following statement:

```
proc mixed data= PASI_in_out1;
by visit;
class <As required factors >;
model change =<As per reqired covarites> /;
lsmeans treatment /diff pdiff cl;
ods output diffs=diff_MI lsmeans=LSM_MI;
run;
```

where prop_score is the same continuous variable used for the primary model.

Results of the ANCOVA analysis on 500 imputed dataset will be combined to derive an overall results using the following code:

proc mianalyze parms(classvar=full)=diff_mi;

class cohort;

modeleffects cohort:

ods output parameterestimates=DIFF_MIAN;

by visit;

run;

proc mianalyze data=lsm_mi;

class cohort;

modeleffects cohort:

ods output parameterestimates=LSM_MIAN;

by visit;

run;

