The choice of the MMRM model instead of a simple ANCOVA model on changes vs week 0 considering the prevalence approach or Last observation carried forward (LOCF) approach was done because the LOCF approach would underestimate the within-group mean changes between treatments compared with MMRM, whereas the prevalence approach tend to overestimate the within-group changes (Prakash et al. 2008).

In addition to that, similar MMRM model will be fitted on LOCF and prevalence set without the propensity score approach. An unstructured covariance matrix for the repeated measures within each patient will be applied in the analysis, if the model does not converge, compound symmetry will be used. The explanatory variables in the longitudinal model include cohort, visit, cohort-by-visit interaction, age, geographical region (i.e. north vs south vs central), BMI categories (<25 vs >=25), waist circumference, smoking status, metabolic syndrome (yes vs no), age at diagnosis of psoriasis, and along with interaction terms of each factor with visit.

The SAS codes are described in appendix section.

MMRM with MI approach

MMRM analysis will be also performed using multiple imputation (MI) approach on ITT population.

The multiple imputation will be done with pattern-mixture models (PMMs) as above, that allows formulating assumptions regarding missing data in a transparent and clinically interpretable manner.

The SAS codes are described in appendix section.

PASI 75

A logistic regression analysis model will be also fitted, considering age, geographical region, BMI, smoking status, metabolic syndrome, TNF α -308 polymorphism (if feasible), as well as all clinical relevant variable resulting statistically different at baseline between cohort, as strata factors. The analyses will be done similar to primary analyses based on prevalence, LOCF and NRI approaches using ITT set.

Time to reach PASI 90

The differences between cohorts Cw6-negative and Cw6-positive in time to reach PASI 90 will be evaluated by means of a log-rank test. The hazard ratios and their corresponding 95% confidence intervals will be also computed using a stratified Cox proportional hazards regression model with Cw6 group and baseline PASI as explanatory variable and stratified by geographical region and BMI categories, as well as age categories (tertiles).

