2.11 Patient-reported outcomes

Variables related to health-related quality of life (HR-QoL) are described below. All HR-QoL variables will be evaluated based on Safety set. Both prevalence and LOCF approach will be adopted.

Dermatology Life Quality Index

Seven scores will be derived from the DLQI: the total score of each of the six dimensions as well as the total score over all items. The higher the score, the more quality of life is impaired.

The percentage change from baseline will be derived for each of the seven scores. Summary statistics will be provided for absolute values as well as for the percentage change by visit.

Changes from baseline in DLQI at each time point will be analyzed by means of a paired ttest or Wilcoxon signed-rank test, based on data distribution.

In addition, summary statistics will be provided for the number of patients achieving DLQI 0 or 1 at each time point specifying absolute and relative frequency of patients with DLQI 0/1 response. Further, comparison between baseline and each time point for proportion of patients achieving DLQI 0 or 1 will be performed using McNemar's test.

Following details to the DLQI scoring: The scoring of each question is as follows

- Very much: scored 3
- A lot: scored 2
- A little: scored 1

- Not at all: scored 0
- Not relevant: scored 0
- Question unanswered: scored 0
- Question 7: "prevented work or studying": scored 3

The DLQI total score will be calculated by summing the score of each question resulting in a maximum of 30 and a minimum of 0. The highger the score, the more quality of life is impaired.

Meaning of DLQI scores:

- 0-1= no effect at all on patient's life
- 2-5= small effect on patient's life
- 6-10= moderate effect on patient's life
- 11-20= very large effect on patient's life
- 21-30= extremely large effect on patient's life

The DLQI will be analyzed under six headings as follows:

- Symptoms and feelings: questions 1 and 2, score maximum 6
- Daily activities: questions 3 and 4, score maximum 6
- Leisure: questions 5 and 6, score maximum 6
- Work and school: question 7, score maximum 3
- Personal relationships: question 8 and 9, score maximum 6
- Treatment: question 10, score maximum 3

Interpretation of incorrectly completed questinnaires:

There is very high success rate of accurate completion of the DLQI. However, sometimes patients do make mistakes.

- 1. If one question is left unanswered this is scored as 0.

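### The sample code in SAP 5.4.3 does not match the SAP text for two secondary analyses: McNemar's test on DLQI 0/1 (wrong table) and the Cox models for time to PASI 90 and 75 (no STRATA statement)

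*SAP*

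**What the plan says.** **DLQI 0/1.** SAP 2.11 states that "comparison between baseline and each time point for proportion of patients achieving DLQI 0 or 1 will be performed using McNemar's test". This is a paired, within-patient question, and the objective (SAP Table 1.2-1) concerns all patients, not a cohort contrast. SAP 5.4.3 then says "The SAS procedure PROC FREQ with EXACT statement equal to MCNEM or AGREE will be used to perform Mc Nemar's test" and gives as the table statement "TABLES trtan*resp". SAP 5.4.1 shows what that table is. It prints the same crossing with a risk-difference option and comments: "From above code, we can get confidence interval for difference of proportion in PASI90 response between cohorts". So `trtan` is the Cw6 cohort.

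**Time to PASI 90 and PASI 75.** SAP 2.7.2 specifies, for both endpoints, a Cox model with Cw6 group and baseline PASI as explanatory variables, "stratified by geographical region and BMI categories, as well as age categories (tertiles". SAP 5.4.3 introduces the code as "computed using a stratified Cox proportional hazards regression model with Cw6 group and baseline PASI as explanatory variable with the following sample SAS code". The block itself has a CLASS statement, then "MODEL var*censor(0)= trtpn base.../rl ties=efron", then RUN. It has no STRATA statement.

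**The concern.** In both places the final SAP describes one analysis in its text and another in its code.

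For McNemar, the printed table has no baseline variable, no visit variable and no BY statement. A programmer who fills in the dataset name and keeps the table gets output that runs without error and prints a p-value. That p-value would answer a question nobody asked, and it would be reported as the test of change in DLQI 0/1.

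For the Cox model, code completed without a STRATA line fits one common baseline hazard to all patients. The hazard ratio for Cw6 would then not be adjusted for region, BMI category and age in the way the text requires. The cohorts are defined by genotype and are not randomised, so balance on these factors cannot be assumed.

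**Working it through.** The documents give no figure for either analysis, so there is no stated result to reproduce. The check has three parts.

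**1. What McNemar's test does on the printed table.** Let rows be POS/NEG and columns responder/non-responder, with cells a = POS responders, b = POS non-responders, c = NEG responders, d = NEG non-responders. The statistic is (b − c)²/(b + c).

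With 219 POS patients and R responders in total, b = 219 − a and c = R − a, so b − c = 219 − R. The test therefore asks whether the number of responders equals the number of Cw6-positive patients. If response is coded the other way, the off-diagonal cells are a and d, and a − d = R − 146. Baseline DLQI appears in neither expression.

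**2. Illustration.** Inputs: 219 POS and 146 NEG, the planned evaluable numbers in SAP section 3. Assumption: the same DLQI 0/1 rate in both cohorts, varied from 40% to 80%.

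At 60%:
- POS non-responders 219 × 0.4 = 87.6 and NEG responders 146 × 0.6 = 87.6. The difference is 0 and p = 1.0.
- Other coding: 219 × 0.6 = 131.4 against 146 × 0.4 = 58.4. (131.4 − 58.4)²/(131.4 + 58.4) = 5329/189.8 = 28.1.

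Exact McNemar p-values, with cells rounded to whole patients:

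| Assumed rate | POS non-resp. vs NEG resp. | p | POS resp. vs NEG non-resp. | p |
|---|---|---|---|---|
| 40% | 131 vs 58 | 1e-7 | 88 vs 88 | 1.0 |
| 50% | 109 vs 73 | 0.009 | 110 vs 73 | 0.008 |
| 60% | 88 vs 88 | 1.0 | 131 vs 58 | 1e-7 |
| 70% | 66 vs 102 | 0.007 | 153 vs 44 | 3e-15 |
| 80% | 44 vs 117 | 8e-9 | 175 vs 29 | 1e-26 |

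For contrast, take the paired baseline-by-visit table and assume that 18 of 365 patients (about 5%) have DLQI 0/1 at baseline and none lose it. At a 40% visit rate, 146 − 18 = 128 patients gain and 0 lose, and the exact p is 2 × 0.5^128, about 6e-39. It is smaller still at the higher rates. So under these assumptions a very large within-patient improvement can come out of the printed table as p = 1.0.

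**3. Cox code against text.** The only ellipses in the PHREG block are in the dataset name, CLASS and MODEL. Filling those in CLASS and MODEL could add covariates, but covariates are not strata. The neighbouring PROC LIFETEST block does carry a STRATA placeholder, so the appendix shows one where it intends one.

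A simulation shows only that the difference can be nil or material. It used 300 data sets per scenario, 219/146 patients, true hazard ratio 1 and follow-up to 24 weeks. Strata were two regions × BMI class × age tertile. The assumed log-hazard effects were −0.3 for region, −0.5 for BMI ≥ 25, −0.2 per age tertile and −0.1 per SD of baseline PASI.

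| Scenario (assumed) | Mean HR, no strata | Mean HR, strata | Rejection at 5%, no strata | Rejection at 5%, strata |
|---|---|---|---|---|
| Imbalanced: region 40% POS vs 60% NEG; BMI ≥ 25 55% vs 70% | 1.15 | 1.01 | 18.7% | 5.3% |
| Balanced | 1.02 | 1.02 | 3.7% | 5.0% |

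In the balanced case, single-trial log hazard ratios still differed by about 0.05 on average.

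**The case against.** The best defence is that this is template code and was never meant to be run as printed. Both blocks are called sample code. The McNemar block names no dataset and offers two alternatives in its EXACT line, and the PHREG block is full of ellipses. Other samples are also loose: the Poisson example in SAP 5.4.3 leaves out exposure, comorbidities and BMI class and cuts age at 40 years, although SAP 2.8.1 asks for all of those and for age tertiles. The body text states the pairing and the strata without ambiguity, the Cox lead-in itself says stratified, and SAP 2.7.2 refers to the appendix code only for the MMRM and multiple-imputation analyses. The DLQI 0/1 frequencies and the paired t or Wilcoxon tests do not depend on the McNemar block.

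Most of this stands, and it is why the point is minor. A reader might infer that the reported p-values and hazard ratios will be wrong. The documents do not support that, because a programmer working from the text would produce the right analyses.

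What the defence does not cover is the McNemar table itself. A sample label excuses placeholder names, but that table statement has no placeholder to complete. Reading `trtan` as time point in stacked data does not help either, because the table would still ignore which records belong to the same patient. The paired t-test block just above uses a before-by-after pair, so the appendix does write paired code correctly elsewhere.

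**Conclusion.** The point holds as a mismatch between sample code and text. It is minor and confined to secondary endpoints.

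- **McNemar.** That the printed table contains no baseline information is read directly from the SAP and rests on no assumption. The p-values above rest on assumed DLQI 0/1 rates and on the planned evaluable numbers, whereas SAP 2.11 analyses DLQI on the Safety set. They show the kind of error, not a forecast.
- **Cox.** The missing STRATA statement is also plain. A reader might infer that the hazard ratios would be biased. That depends on how far the cohorts differ in region, BMI and age and on how strongly these factors affect response, and the documents give neither. The 1.15 comes entirely from assumed values, and in the balanced scenario the mean hazard ratios agree.
- **Baseline PASI.** A reader might also infer that the Cox code fits baseline PASI as a class variable with one level per score. This is not established: CLASS names `baseline`, MODEL names `base` followed by an ellipsis, and the SAP defines neither. At most, the two names should be made consistent.

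The primary analysis is not touched by this point. In SAP 5.4.1 the cohort-by-response table is the right one for a difference between cohorts.

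**What to change.** Correct the two blocks in SAP 5.4.3:

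- **McNemar:** use one record per patient and visit, holding that patient's baseline and visit DLQI 0/1 status, then `BY visit; TABLES base_dlqi01*visit_dlqi01 / AGREE; EXACT MCNEM;`.
- **PHREG:** add `STRATA region bmi_cat age_tertile;` as SAP 2.7.2 requires, and use the same variable name for baseline PASI wherever it appears in the block.

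The cost is a few lines of appendix code. No data collection, endpoint, analysis set or sample size changes, and the body text of SAP 2.7.2 and 2.11 can stay as it is on these points.
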